### **11.2.2. Control of Systematic Error/Bias**

Registry is open to subjects planning to undergo a procedure with the Flexiva Pulse and Flexiva Pulse ID Laser Fibers for any indication per the IFU and at multiple centers. All subjects will be treated according to the directions in the Operating Manual and IFU/DFU. The primary safety endpoint analysis which is based on the exact Clopper-Pearson confidence interval is specified to be conservative in nature.

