**Figure 7.1-1: Flexiva Pulse Laser Fiber Post-Market Registry Study Design**

## 7.2. Treatment Assignment

This is a post-market registry study. Any subject who is indicated for lithotripsy or BPH undergoing HoLEP and is willing to provide a written informed consent will be approached and considered for enrollment in the study. The subject is considered enrolled in the study once the subject has signed the informed consent form and the lithotripsy/HoLEP procedure is attempted. Each subject will be assigned a unique subject identifier in the Electronic Data Capture (EDC) system.

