## 8. Subject Selection

### 8.1. *Study Population and Eligibility*

Approximately 200 subjects will be enrolled and treated for lithotripsy of urinary calculi and BPH indications. There will be about 100 subjects enrolled in the lithotripsy cohort and 100 subjects enrolled in the BPH cohort.

Subjects will generally be recruited from physician's practice. Subjects who meet all of the inclusion criteria (see **Table 8.2-1**) and none of the exclusion criteria (see Section 8.3) may be given consideration for inclusion in this clinical investigation.

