## **10.2. Study Candidate Screening**

All interested subjects will undergo screening during which their eligibility for the study will be determined. Sites are expected to follow standard of care testing to diagnose and screen subjects for inclusion in the study.

Subjects who do not meet the inclusion/exclusion criteria are considered screen failures.

If the subject has completed the informed consent process and met all inclusion and none of the exclusion criteria, the subject will progress to the Lithotripsy/HoLEP procedure and follow-up phase of the study.

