### **11.2.3. Number of Subjects per Investigative Site**

The study will be conducted at up to 10 sites. Sites will be encouraged to enroll a minimum of 5 subjects per procedure cohort. A maximum of 25 subjects per procedure cohort may be enrolled at a site, unless the site has received prior approval from the sponsor to enroll additional subjects.

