**Table 23.2-1: Definitions**

Term	Definition
Adverse Device Effect (ADE)	See Table 17.2-1: Safety Definitions
Adverse Event (ADE)	See Table 17.2-1: Safety Definitions
As Treated	All subjects for whom treatment is attempted.
Clinical Events Committee	An independent or group of physicians with trial relevant therapeutic expertise whose purpose is to review and adjudicate important endpoints and/or specific adverse events.
Data Subject	In GDPR: Any living individual to whom the personal data relates. Examples of data subjects in this study are physicians and subjects.

Term	Definition
Deviation (Clinical Protocol)	A departure from the requirements established in the clinical trial protocol (e.g., inclusion/exclusion criteria; visit windows, required procedures, and any specified consenting process requirements).
Device Deficiency	See Table 17.2-1: Safety Definitions
General Data Protection Regulation (GDPR)	The General Data Protection Regulation (GDPR) is a European law that will govern how companies (whether EU-based or not) use personal data.
Hospitalization	See Table 17.2-1: Safety Definitions
Intent-To-Treat	A subject who signs the informed consent, meets eligibility criteria, and for whom the Lithotripsy/HoLEP procedure is initiated but not completed (first incision). The original ICF and screening documentation for intent to treat patients should be maintained in the site's files. These patients are followed in accordance with the study follow up schedule for safety and count toward enrollment.
Monitoring	EN ISO 14155:2020-3.29 - Act of overseeing the progress of a clinical investigation to ensure that it is conducted, recorded, and reported in accordance with the CIP, written procedures, this document, and the applicable regulatory requirements.  ICH E6 1.38 - The act of overseeing the progress of a clinical study and of ensuring that it is conducted, recorded, and reported in accordance with the protocol, Standard Operating Procedures (SOPs), GCP, and the applicable regulatory requirement(s).  FDA Guidance - Generally refers to the methods used by sponsors of investigational studies, or CROs delegated responsibilities for the conduct of such studies, to oversee the conduct of and reporting of data from clinical investigations, including appropriate investigator supervision of study site staff and third-party contractors.

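### The only statistical measure listed as bias control in section 11.2.2, a conservative exact interval, addresses sampling error; with no consecutive-enrollment rule or log of unenrolled eligible patients, representativeness cannot be verified

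*Combined protocol and SAP*

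**What the plan says.** Section 11.2.2 (Control of Systematic Error/Bias) contains three statements:

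1. Open entry: "Registry is open to subjects planning to undergo a procedure with the Flexiva Pulse and Flexiva Pulse ID Laser Fibers", for any labeled indication and at several centers.
2. Uniform use: "All subjects will be treated according to the directions in the Operating Manual and IFU/DFU".
3. The interval: "The primary safety endpoint analysis which is based on the exact Clopper-Pearson confidence interval is specified to be conservative in nature".

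On who enters the registry and who is recorded:

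- Section 7.2: any patient indicated for lithotripsy, or with BPH and undergoing HoLEP, who is "willing to provide a written informed consent will be approached and considered for enrollment in the study".
- Section 8.1, repeated in 8.2: eligible subjects "may be given consideration for inclusion in this clinical investigation".
- Section 10.2: a consented, eligible subject goes on to the procedure and follow-up. "Subjects who do not meet the inclusion/exclusion criteria are considered screen failures"; no count or log of them is asked for.
- Section 9.2 requires accounting for enrolled subjects. Enrollment (section 9.1) needs both consent and an attempted procedure.
- Table 23.2-1, under Intent-To-Treat: "The original ICF and screening documentation for intent to treat patients should be maintained in the site's files".
- Section 11.2.3: "A maximum of 25 subjects per procedure cohort may be enrolled at a site", unless the sponsor approves more.

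**The concern.** A property that concerns random error is offered under a heading about systematic error. The registry has no comparator and no hypothesis test (section 11.1.1.1), and its stated aim is safety and performance in routine use (sections 4.2 and 7.3). The value of its estimates therefore rests on how well the enrolled subjects represent the patients treated with these fibers.

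If harder cases were offered enrollment less often, the SADE rate would come out too low, and stone-free rates and IPSS change would probably look too good. Nothing the protocol requires would show this. A reader who takes section 11.2.2 at its word would believe that the interval guards against it.

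**Working it through.** **Inputs from the plan** (sections 11.1.1.2 and 11.1.1.3): 90 evaluable subjects per cohort; assumed SADE rates of 3% (lithotripsy) and 5% (BPH); two-sided 95% Clopper-Pearson interval; stated widths 8.4% and 10.2%; 10% attrition; 100 treated per cohort.

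**Step 1. Reproduce the plan's figures.** The lower limit is the 2.5% quantile of Beta(x, n − x + 1). The upper limit is the 97.5% quantile of Beta(x + 1, n − x).

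- Lithotripsy: x = 90 × 0.03 = 2.7; limits 0.55% and 8.95%; width 8.40%.
- BPH: x = 90 × 0.05 = 4.5; limits 1.52% and 11.75%; width 10.23%.
- Treated: 90 / (1 − 0.10) = 100.

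The plan's figures are correct.

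**Step 2. What the conservatism provides.** Actual coverage at n = 90 is the binomial probability that the interval contains the rate in the enrolled population. It is 98.1% at 3% and 97.6% at 5%. Against the nominal 95%, that is 3.1 and 2.6 points of extra coverage. The calculation takes the enrolled rate as the target, so it says nothing about the gap between that rate and the rate among all eligible patients.

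**Step 3. Illustration of a shift (risks and mix are assumptions).** Take a practice with half easy cases at 1% SADE risk and half hard cases at 5%.

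- All patients: 0.5 × 1% + 0.5 × 5% = 3.0%.
- Enrolling 80% easy cases: 0.8 × 1% + 0.2 × 5% = 1.8%.
- Difference: 1.2 points, or 1.2 / 3.0 = 40% relative.

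**Step 4. A second model over a range.** Suppose a fraction f of eligible patients is not enrolled and has RR times the SADE risk of those enrolled. Then enrolled rate = all-eligible rate / ((1 − f) + f × RR). Both f and RR are assumptions.

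| f, RR | Divisor | BPH enrolled rate (true 5%) | Coverage of 5% | Upper limit below 5% | Lithotripsy enrolled rate (true 3%) |
|---|---|---|---|---|---|
| none | 1.0 | 5% | 97.6% | 1.0% | 3% |
| 20%, 2 | 1.2 | 4.17% | 97.4% | 2.2% | 2.50% |
| 30%, 3 | 1.6 | 3.125% | 94.2% | 5.7% | 1.875% |
| 50%, 5 | 3.0 | 1.67% | 78.0% | 22.0% | 1.00% |

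In lithotripsy, coverage of 3% stays at 99% or more in the selected scenarios, because even 0 events in 90 gives an upper limit of 4.0%. The harm there is to the point estimate, not to coverage.

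**Step 5. What the protocol leaves on record.**

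| Patient | Record required by the protocol |
|---|---|
| Eligible, never approached | None |
| Approached, declined | None |
| Screen failure | Category defined (10.2), no log |
| Consented, procedure attempted | Accounted for (9.2; Table 23.2-1) |

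The first two rows are where selection would occur.

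**The case against.** Several points on the other side carry weight.

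- **A reader might infer that bias control rests wholly on the interval.** It does not. Section 11.2.2 names open eligibility and labeled use first. Other sections add independent adjudication (19.2), a primary ITT analysis (11.2.1), a site cap (11.2.3) and Fisher's exact test across sites (11.3.5). This stands. But adjudication deals with event classification, ITT starts after enrollment, the cap limits one site's weight, and Fisher's test sees enrolled subjects only and would miss selection common to all sites. None shows who was left out.
- **A reader might infer that investigators may pick their cases.** The text does not say so. Section 7.2 applies to any indicated, willing patient, and section 10.2 moves eligible, consenting subjects forward. What remains is narrower: willingness is known only after an approach, sections 8.1 and 8.2 use weaker wording, and compliance cannot be checked.
- **A reader might infer that the interval is not even conservative for random error**, since four sites at the cap of 25 could fill a cohort (4 × 25 = 100). With an assumed intraclass correlation of 0.05, simulated coverage at four sites is 92.8% (3% rate) and 88.9% (5% rate). But the plan is for up to 10 sites, where the same assumption gives 95.9% and 94.4%. The documents give no intraclass correlation, and a site homogeneity test is already planned. This reading is not supported, and no clustering analysis is asked for.
- **A log may be required elsewhere.** The monitoring plan and the Clinical Study Agreement are not part of the document. The point is therefore that the protocol does not require one, not that none exists.
- **The shift may be small beside the imprecision.** In the first illustration it is 1.2 points against a planned width of 8.4%. This is fair, but a wide interval does not make the point estimate representative.

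**Conclusion.** The point holds in limited form. It needs no assumption to say that Clopper-Pearson conservatism is not a control of systematic error, and that the protocol neither states consecutive enrollment nor requires a record of eligible patients who were not enrolled. Representativeness of the SADE and efficacy estimates therefore cannot be verified from what the protocol collects.

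The documents do not show that selection will occur or how large it would be. The move from 3.0% to 1.8%, and the BPH range from 4.17% down to 1.67% against 5%, depend entirely on the assumed risks, mix, f and RR. The 78.0% coverage is the extreme of that range. The planned interval, its width and the sample size are sound for what they measure.

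**What to change.** - **Section 11.2.2:** remove the Clopper-Pearson sentence as a bias control. The method stays in section 11.1.1.3 as the interval for the SADE rate. In its place, state that sites offer enrollment to consecutive eligible patients scheduled for a Flexiva Pulse procedure until the site cap is reached.
- **Sections 7.2, 8.1 and 8.2:** align the wording with that rule.
- **Log:** require each site to keep a de-identified count of patients eligible, approached, consented and attempted, with reasons for each loss.
- **Reporting:** show the enrolled fraction (attempted / eligible) by site and cohort beside the SADE rate.

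Cost: amended wording, a short site log and one extra table, with a small site workload. Sample size, interval width, endpoints and treatment do not change. The log should run alongside enrollment, because counts of patients never approached are hard to rebuild reliably afterwards.

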### **11.2.3. Number of Subjects per Investigative Site**

The study will be conducted at up to 10 sites. Sites will be encouraged to enroll a minimum of 5 subjects per procedure cohort. A maximum of 25 subjects per procedure cohort may be enrolled at a site, unless the site has received prior approval from the sponsor to enroll additional subjects.

## **11.3. *Data Analyses***

The analyses will include the available cases only unless specified otherwise. Presentation of summary statistics for continuous variables will include N, mean, median, standard deviation, minimum, and maximum values. For categorical variables, the number and percentage under each category will be presented

### **11.3.1. Secondary Endpoints**

#### **11.3.1.1. Secondary Safety Endpoint – Procedure related adverse events and/or adverse device effects**

This endpoint applies to both procedure cohorts. Procedure related adverse events and/or adverse device effects related to Flexiva Pulse Laser Fibers including but not limited to:

- Perforation
  - For HoLEP procedures: in prostate capsule, bladder, and/or urethra
  - For Lithotripsy procedures: anywhere in urinary tract
- Hemorrhage resulting in blood loss of  $\geq 500\text{mL}$
- Burn

##### ***11.3.1.1.1 Statistical Methods***

For each procedure cohort, summary statistics will be calculated for overall device and/or procedure related AEs, and for the device and/or procedure related perforation, hemorrhage and burn effects, respectively. The summary statistics includes but not limited to event count, event rate by seriousness procedure relatedness, and device relatedness.

#### **11.3.1.2. Secondary Efficacy Endpoint 1 – Ability of the laser fiber to deliver energy**

This endpoint applies to both procedure cohorts. This endpoint is measured by whether or not the index procedure was successfully completed as indicated.

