Secondary Efficacy Endpoints	
For Lithotripsy procedures:
 

Ability of the laser fiber to deliver energy (successful completion of lithotripsy procedure as indicated)

Compatibility of the laser fiber with endoscope (including successful passage and maneuverability without fracture)

 
For HoLEP procedures:
 

Improvement in Quality of Life (QoL) from baseline as measured by favorable change in International Prostate Symptom Score (IPSS) at 3-month follow-up

Improvement in uroflowmetry from baseline as measured by change in maximum urinary flow rate (Qmax) at 3-month follow-up

Hemostasis measured by ability to coagulate during HoLEP procedure

Ability of the laser fiber to deliver energy (successful completion of HoLEP procedure as indicated)

Compatibility of the laser fiber with endoscope (including successful passage and maneuverability without fracture)

Additional Endpoint	Fiber tip degradation
Method of Assigning Patients to Treatment	This is an open label, non-randomized study
Follow-up Schedule	
For Lithotripsy cohort:
 

Baseline: Pre-procedure imaging study report within 60 days prior to procedure

Lithotripsy Procedure(s): Laser surgery for stone fragmentation/removal

All follow-up visits within 2 months (60 days) of discharge from final holmium laser lithotripsy procedure per site's Standard of Care (SOC)

Flexiva Pulse Laser Fiber Post-Market Patient Registry Flexiva Pulse Registry	
	For BPH cohort: 

• Baseline

• HoLEP Procedure

• All follow-up visits within 6 months (180 days + 60 days) of discharge from HoLEP procedure per site's SOC

Study Duration	Enrollment is expected to be completed in approximately 12 months; therefore, the total study duration is estimated to be approximately 20 months.
Participant Duration	The study duration for each subject in the Lithotripsy cohort is expected to be up to 2 months (60 days) post discharge from final holmium laser lithotripsy procedure. The study duration for each subject in the BPH cohort is expected to be up to 6 months (180 days + 60 days) post discharge from HoLEP procedure.

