#### **4.2. *Study Rationale***

Ureteroscopy became a mainstay of urolithiasis treatment as smaller, more flexible endoscopes became available that are used in conjunction with holmium laser fibers that can fit and bend in these flexible endoscopes. The holmium laser fibers come in varying sizes. In general, larger core fibers (550-1000  $\mu\text{m}$  sizes) are used in a straight configuration with endoscopes used in PCNL procedures; whereas, smaller core fibers ( $\leq 365 \mu\text{m}$ ) have the greater flexibility required for flexible ureteroscopy (fURS) procedures.

Holmium laser enucleation of the prostate (HoLEP) is a minimally invasive surgical procedure for the treatment of BPH. During a HoLEP procedure, a holmium laser fiber (usually 550  $\mu\text{m}$  size) is passed through an endoscope and used to deliver holmium laser energy for enucleation and removal of enlarged prostate tissue away from the prostatic capsule.

Selecting the right fiber size, and its impact on fiber flexibility and flow rates helps in understanding performance of the fiber during clinical use. However, fiber performance and safety data in a clinical setting is limited. The objective of the Flexiva Pulse registry is to collect on-going post-market safety and performance data for the Flexiva Pulse and Flexiva Pulse ID Laser fibers in routine clinical use.

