#### **10.6. *Lithotripsy/HoLEP Procedure Visit***

Lithotripsy/HoLEP procedure is defined as the start time of sedation and/or anesthesia and includes the entirety of the holmium laser Lithotripsy or HoLEP procedure. The procedure will be performed by a trained physician and per the Flexiva Pulse Laser Fiber IFU.

It is recommended that surgeons perform a second evaluation at the time of the lithotripsy procedure to ensure all stones have been removed.

If multi-staged lithotripsy procedures are performed using the Flexiva Pulse Laser Fibers, then data will also be collected on the additional procedures. **If the additional lithotripsy procedure performed does not use the Flexiva Pulse Laser Fibers, then subject should be exited from the study at the time of the additional procedure.**

If subject is undergoing HoLEP and simultaneous holmium laser lithotripsy using Flexiva Pulse Laser Fibers to remove bladder calculi, data will also be collected on the lithotripsy procedure.

Baseline visit information may be collected on same day, prior to the Lithotripsy/HoLEP procedure.

After the Lithotripsy/HoLEP procedure, the following data will be collected:

- Procedure information and evaluation of applicable BSC devices used. It is recommended that User Feedback Evaluations are **completed within 1 week of procedure.**
- Fiber Information – type, size, number of fibers used, model of scope, number of passes per fiber, fiber fracture, fiber deflection, if fiber was stripped/cleaved
- Fiber Performance – fiber tip degradation
- Assessment of adverse events and device deficiencies
- COVID-19 assessment: prior diagnosis, test result, vaccination status (if available)

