#### *11.3.1.2.1 Statistical Methods*

For each procedure cohort, the proportion of subjects who had successful completion of the index procedure will be estimated.

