#### *11.3.1.3.1 Statistical Methods*

The proportion of fibers which are compatible with the endoscope among all the fiber used in the index procedure will be estimated.

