### ***17.5. BSC Device Deficiencies***

Device deficiencies will be collected for BSC devices only and will be documented and reported to BSC. If possible, the device(s) should be returned to BSC for analysis. Instructions for returning the device(s) will be provided by the Clinical Project Manager. Device deficiencies should also be documented in the subject's source records.

Device deficiencies are not adverse events. However, an adverse event that results from a device deficiency, would be recorded as an adverse event on the appropriate eCRF.

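### Secondary Efficacy Endpoint 1 is named for the fiber's energy delivery but scored by procedure completion, so it misses failures remedied by a replacement fiber and cannot attribute the rest

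*Combined protocol and SAP*

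**What the plan says.** The synopsis lists the lithotripsy endpoint as "Ability of the laser fiber to deliver energy (successful completion of lithotripsy procedure as indicated", with a matching HoLEP entry, and Table 6-1 repeats both. Section 11.3.1.2 applies one definition to both cohorts: "This endpoint is measured by whether or not the index procedure was successfully completed as indicated". Section 11.3.1.2.1 fixes the unit of analysis: for each cohort, "the proportion of subjects who had successful completion of the index procedure will be estimated". The documents do not say what makes a completion successful, or how a failed or exchanged fiber is scored.

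Fiber-level data are collected. Section 10.6 lists "Fiber Information – type, size, number of fibers used, model of scope, number of passes per fiber, fiber fracture" among the items recorded after the procedure. The neighbouring compatibility endpoint is analysed per fiber (Section 11.3.1.3.1): "The proportion of fibers which are compatible with the endoscope among all the fiber used in the index procedure will be estimated". Section 17.5 adds: "Device deficiencies will be collected for BSC devices only and will be documented and reported to BSC". Section 11 plans no summary of those deficiencies.

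Section 11.2.1 makes ITT (every attempted procedure) the primary set and repeats efficacy endpoints in the per-protocol (PP) set. PP is drawn from the As Treated (AT) set, which that section limits to completed procedures.

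**The concern.** The label describes a property of the device, but the measure describes the fate of the operation. The two come apart in both directions. A fiber can fail while the operation succeeds, because another fiber is opened. An operation can also fail while the fiber works, for example through loss of access or visibility.

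Section 4.2 justifies the registry on the ground that "fiber performance and safety data in a clinical setting is limited". A percentage reported under the name of energy delivery will be read as evidence on that question. If exchanges for failure occur, the percentage will overstate how reliably individual fibers transmit energy. The analysis offers no way to tell which non-completions were due to the fiber.

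**Working it through.** The plan states no expected rate, target or interval for this endpoint, so there is no figure to reproduce. The sizing in Section 11.1.1.2 concerns serious adverse device effects only.

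**1. Scoring under the text as written**

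| Event in the index procedure | Did the fiber deliver energy? | Score under 11.3.1.2 |
|---|---|---|
| First fiber used throughout, case finished | Yes | Success |
| Fiber stops transmitting, second Flexiva Pulse finishes | First fiber: no | Success |
| Fiber stops transmitting, another make of fiber finishes | No | Success |
| Fiber stops transmitting, case abandoned | No | Failure |
| Case abandoned for a non-fiber reason | Yes, or not tested | Failure |

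Rows 2 and 3 follow from the definition and the absence of an exchange rule; the plan does not state them outright. On row 3, Sections 10.6 and 10.10 deal with non-Flexiva fibers only in additional staged lithotripsy procedures, not in a switch within the index procedure. On row 5, Section 10.6 starts the procedure at sedation or anesthesia, so a case stopped before any fiber is used could count as a failure.

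**2. Whether another Section 11 analysis fills the gap**

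- Compatibility (11.3.1.3) is per fiber, but covers passage, handling and fracture.
- Hemostasis (11.3.1.6) depends on energy, but is HoLEP-only and per subject, so an exchange can mask a failure there too.
- Tip degradation (11.3.2.1) is a subjective rating against the physician's current fiber.
- Device deficiencies have no planned summary.

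None measures energy delivery per fiber.

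**3. Sensitivity analysis**

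Under Section 11.2.1, PP lies within AT, and every AT subject has a completed procedure. The PP proportion can fall below 100% only through subjects whose procedure was completed but not judged successfully completed. Table 23.2-1 instead describes As Treated as everyone in whom treatment was attempted. The by-construction result rests on the Section 11.2.1 definition.

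**4. Illustration of size**

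Assumptions, none from the documents: failure probability q per fiber, independent failures, one spare, no other cause of non-completion. Both fibers must fail to stop the case, so completion = 1 − q².

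| q | First-fiber success, 1 − q | Completion, 1 − q² | First-fiber failures per 100 subjects | Endpoint failures per 100 |
|---|---|---|---|---|
| 2% | 98% | 99.96% | 2 | 0.04 |
| 5% | 95% | 99.75% | 5 | 0.25 |
| 10% | 90% | 99.0% | 10 | 1 |
| 20% | 80% | 96.0% | 20 | 4 |

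For 100 subjects at q = 10%, the exact 95% interval is 94.6% to 99.97% for 99/100 completions, against 82.4% to 95.1% for 90/100 first-fiber successes.

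**5. What a fiber-level denominator recovers**

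In the same example, 100 first fibers plus 10 spares make 110 fibers used, with 10 + 1 = 11 failures. 11/110 = 10%, which is q.

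**6. Attribution**

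Let a share r of cases stop for non-fiber reasons, independently. Completion is then (1 − q²)(1 − r). With q = 10% and r = 0 it is 99%. With q = 0 and r = 1% it is also 99%. The endpoint cannot tell these apart.

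**The case against.** The best defence is that completion is an explicit, consistently stated surrogate for a secondary, descriptive endpoint. Section 11.1.2.1 says there is no hypothesis, and the main objective is addressed first by serious adverse device effects, stone-free rate and IPSS. Much of this stands, and it rules out several stronger readings.

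- A reader might infer that the endpoint cannot detect fiber failure at all. It can: a failure that ends the procedure is scored as non-completion, though not attributed to the fiber.
- A reader might infer that the registry is blind to fiber failure. It is not: fracture and fiber counts are recorded, and Table 17.4-1 requires device deficiencies to be reported within 3 calendar days. The gap is in how this endpoint is defined and analysed.
- A reader might infer that the result will be near 100% whatever the true failure rate, with most failures unrelated to the fiber. The first part depends on assumed values. The second has no support in the documents, and the illustration sets non-fiber causes to zero.
- A reader might infer that the performance objective goes unanswered. One imprecise secondary endpoint does not imply that.

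Two cautions also stand. Recording the number of fibers does not show that extra fibers were opened because of failure; Section 4.2 describes different sizes for different uses. The procedure and user-feedback forms are not in the documents, so the reason for opening another fiber may already be captured.

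The defence does not close the mismatch between label and measure, or supply the missing exchange rule.

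**Conclusion.** The point holds in a limited form. As written, Secondary Efficacy Endpoint 1 misses any fiber failure remedied by opening another fiber, does not require completion with a Flexiva Pulse fiber, and cannot separate fiber-caused non-completion from other causes. No other planned analysis measures energy delivery per fiber, and the PP repeat adds almost nothing under the Section 11.2.1 definitions.

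The size is unknown. If failures were independent at 10% per fiber, with one spare and no other cause of non-completion, the endpoint would read 99%, against 90% of first fibers working. The primary endpoints are untouched, but the correction is cheap and should be made before analysis.

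**What to change.** 1. **Keep completion under its own name**, as a subject-level outcome in ITT.
2. **Define energy delivery per fiber**, using the kind of denominator Section 11.3.1.3.1 already has: of all Flexiva Pulse fibers used in the index procedure, the proportion not exchanged or abandoned for loss of transmission, fracture or another device deficiency. Count an exchange for a planned size change as a non-failure. Tabulate exchanges for tip wear separately.
3. **Add a subject-level companion**: the proportion of subjects whose procedure was completed with no fiber exchanged for failure and no switch to a non-Flexiva fiber. List procedures stopped for non-fiber reasons by reason, and show the rate with and without them in the denominator.
4. **Add a planned summary of device deficiencies** to Section 11.
5. **Record the reason for opening each further fiber**, if the CRF does not already do so.

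The synopsis and Table 6-1 need matching wording. If an interval is given for the per-fiber proportion, it should allow for several fibers from one subject. The cost is slightly more analysis, possibly one CRF field, and a percentage that may look less favourable. Fiber counts, fracture and deficiencies are already collected.
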